#### 7.5 Data management

#### 7.5.1 Data collection

Designated Investigator staff will enter the data required by the protocol into the eCRFs using fully validated secure web-enabled software that conforms to US CFR 21 Part 11 requirements. Designated Investigator site staff will not be given access to the system until they have been trained.

Automatic validation procedures within the system check for data discrepancies during and after data entry and, by generating appropriate error messages, allow the data to be confirmed or corrected online by the designated Investigator site staff. The Investigator must certify that the data entered into the eCRFs are complete and accurate. After database lock or when a site is closed, the Investigator will archive the copies of the patient data at the investigational site.

The Principal Investigator is responsible for assuring that the data entered by the site personnel into the CRF is complete, accurate, and that entry and updates are performed in a timely manner.

#### 7.5.2 Database management and quality control

Novartis personnel or designated CRO personnel will review the data entered by study site staff for completeness and accuracy. Electronic data queries stating the nature of the problem and requesting clarification will be created for discrepancies and missing values and sent to the investigational site via the EDC system. Designated Investigator/site staff is required to respond promptly to queries and to make any necessary changes to the data.

Concomitant medications entered into the database will be coded using the WHO Drug Reference List (WHO\_DRL), which employs the ATC classification system.

Concomitant procedures, non-drug therapies and adverse events will be coded using the Medical dictionary for regulatory activities (MedDRA) terminology.

The occurrence of relevant protocol deviations will be determined. After these actions have been completed and the database has been declared to be complete and accurate, it will be locked and made available for data analysis. Any changes to the database after that time can only be made after written agreement by Novartis.

Confidential

#### 7.6 Data analysis

All analyses will be performed by Novartis or a designated CRO.

An interim safety analysis will be performed for the first 50 patients and a quarterly interim safety report will be submitted to the Indian Regulatory Authority, as per their requirements. A complete analysis will be done after all enrolled patients complete the 56 weeks study period or discontinue the study prior to week 56.

#### 7.6.1 General statistical considerations

Summary statistics for continuous variables will include the number of observations (n), arithmetic mean, standard deviation (SD), minimum, lower quartile, median, upper quartile and maximum. Categorical variables will be presented with absolute and relative frequencies. In addition, key results will be presented with two-sided 95% confidence intervals and p-values for within-subject changes across time.

If no post-baseline value is available for a parameter, then the patient will be removed from the analysis of this parameter. Otherwise, if at least one post-baseline value is available, missing values will be imputed by the last observation carried forward (LOCF) principle regardless of the reason for missing data. Apart from specific summaries and analyses described below, all CRF data will be listed.

#### 7.6.2 Analysis sets

The Full Analysis Set (FAS) will consist of all patients who provided informed consent and are treated with brolucizumab in this interventional study. All effectiveness and safety analyses will use the FAS population.

#### 7.6.3 Patient demography and other baseline characteristics

Demographics and other baseline characteristics will be collected at the first visit prior to the start of brolucizumab treatment. Descriptive statistics (as described under section 7.6.1 "General statistical considerations" above) will be presented for continuous variables.

The following variables will be summarized with descriptive statistics as outlined above: age, gender and baseline values of BCVA, baseline risk factors and ocular related history, and vital signs.

Furthermore, the number (%) of patients will be summarized for prior nAMD treatments by WHO-DRL preferred term, for relevant medical histories by MedDRA primary system organ class and preferred term, and for other ocular conditions by type of condition.

#### 7.6.4 Treatments

A data listing of the study drug (brolucizumab) received by the patient will be provided, and the proportion of participants receiving treatment will be summarized by visit. Exposure to study medication will be summarized by the duration (in days) from start to end of treatment within this interventional study. The number (%) of patients who discontinue prematurely prior to 56 weeks will be tabulated including the reasons for discontinuation. Furthermore, the number of injections will be presented for the total study period.

In addition, the number and percentage of participants receiving rescue medications, concomitant medications, and significant non-drug therapy will be summarized by preferred term (coded by WHO ATC classification) and the same shall be listed.

#### 7.6.5 Safety and Effectiveness analysis

#### **Primary Endpoint Analysis**

• Incidence and characteristics of treatment-emergent adverse events during the 56 weeks of treatment with brolucizumab would be evaluated.

Safety of brolucizumab treatment will be assessed by reported (ocular and systemic) adverse events (AEs). The incidence of AEs (new or worsened after the start of brolucizumab) will be summarized by MedDRA primary system organ class and preferred term. Similar summaries will be provided for fatal AEs and other serious AEs, AEs causing discontinuation of study drug, and AEs suspected to be related to the study medication (as assessed by the Investigator). Furthermore, AEs will be summarized by primary system organ class, preferred term and severity. Incidence rates will also be determined per treatment year, both for the first occurrence of an event and total events. An adverse event management protocol/mitigation plan would be provided to all the investigators to manage an event of intra-ocular inflammation.

#### Secondary Endpoints Analysis

The secondary endpoints will evaluate the effectiveness of brolucizumab in terms of change in the following parameters from Baseline to the end of week 56. BCVA at baseline, week 16 and 56 including the change will be summarized with standard descriptive statistics.

- Mean change in BCVA from baseline to week 16 and week 56 as measured by ETDRS letters.
- Percentage (%) of patient eyes with gain in BCVA of 15/10/5 ETDRS letters or more at week 16 and week 56
- Percentage (%) of patient eyes with loss in BCVA of 15/10/5 ETDRS letters or more at week 16 and week 56.
- Number of anti-VEGF injections, non-injection visits and total number of visits
- Percentage (%) of patient eyes with at least one duration of interval between injections ≥ 8 weeks but <12 weeks.

- Percentage (%) of patient eyes with at least one duration of interval between injections ≥ 12 weeks.

- Percentage of patients with absence of intra-retinal fluid from baseline to week 16 and week 56.
- Percentage of patients with absence of sub-retinal fluid from baseline to week 16 and week 56.
- Estimated change in CST (in µm) from baseline to week 16 and week 56.

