#### 6.2 Secondary Objectives

- 1. To evaluate the effectiveness of brolucizumab in the management of nAMD in terms of change in best-corrected visual acuity (BCVA) from baseline to Week 56.
- 2. Characterize the number of anti-VEGF injections, number of non-injection visits, and total number of visits during the 56 weeks of treatment with brolucizumab.
- 3. Estimate the percentage (%) of patient eyes with anti-VEGF injection intervals q8w and q12w during the 56 weeks of treatment with brolucizumab.
- 4. Estimate effect of brolucizumab on fluid from baseline to week 16 and week 56.
- 5. Estimate effect of brolucizumab on central subfield thickness (CST) from baseline to week 16 and week 56.

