#### 7.2 Setting

The study population will consist of adult male and female outpatients aged 50 years and above, diagnosed with nAMD for whom the treating physician (Investigator) prescribes treatment with brolucizumab 6 mg injection in adherence with the local Summary of Product Characteristics (SmPC) or Prescribing Information (PI). The treatment with brolucizumab should not have been be prescribed for the purpose of entering a patient in this interventional study, but solely based on the clinical judgment of the treating physician. Patients will be considered eligible for this study only after the decision to prescribe brolucizumab has been made as per the treating physician's clinical judgement. The patients should have provided voluntary informed consent to participate in the study.

Brolucizumab 6 mg will be administered by IVT injection as per the Prescribing information (PI) and in line with the treating physician's clinical judgement. Patients will receive loading doses of brolucizumab at Day 0/Visit 1, Week 4/Visit 2 and Week 8/Visit 3. After the loading doses, at Week 16, disease activity assessment (DAA) will be performed based on BCVA and OCT to assess whether the patient will require q8w or q12w dosing.

Patients who are scheduled for q8w dosing with brolucizumab will receive injections at weeks 16, 24, 32, 40, 48.

Patients who are scheduled for q12w dosing of brolucizumab will receive injections at weeks 20, 32, and 44.

DAA will be conducted as per the q8w and q12w dosing administration. Allocation and reallocation to q8w/q12w dosing regimen will be as per Investigator's discretion.

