#### Derivations:

If the question from eCRF "Select Dosing Schedule" is answered as "q12w Dosing" and the duration of interval between injections is above or equal to 12 weeks.

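### Endpoints 3.1 and 3.2 use exact 8- and 12-week cut-offs despite ±1-week visit windows, and the protocol and SAP derive them differently, so 3.1 has two possible readings and some in-window q12w intervals count nowhere

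*Protocol*

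**What the plan says.** Objective 3 (Protocol 6.2) is to "Estimate the percentage (%) of patient eyes with anti-VEGF injection intervals q8w and q12w during the 56 weeks of treatment with brolucizumab". Protocol 7.1.2 and 7.6.5 answer it with two per-eye percentages. Endpoint 3.1 is "Percentage (%) of patient eyes with at least one duration of interval between injections ≥ 8 weeks but <12 weeks". Endpoint 3.2 is "Percentage (%) of patient eyes with at least one duration of interval between injections ≥ 12 weeks". Neither carries a tolerance or a condition on the assigned regimen.

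Protocol 7.2 sets the nominal schedule: "Patients will receive loading doses of brolucizumab at Day 0/Visit 1, Week 4/Visit 2 and Week 8/Visit 3"; then "Patients who are scheduled for q8w dosing with brolucizumab will receive injections at weeks 16, 24, 32, 40, 48", or "Patients who are scheduled for q12w dosing of brolucizumab will receive injections at weeks 20, 32, and 44". The investigator may reallocate an eye between regimens. Table 7-1 (Protocol 7.3.7) gives every visit from Week 4 to Week 48 a window of ±1 week.

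The SAP repeats the protocol definitions in 3.2 (items 3a and 3b) and in the headings and statistics of 20.5 and 20.6. Its derivations differ. SAP 20.5.1 counts an eye in 3.1 only if the eCRF dosing schedule is q8w and the interval is 8 to 11 weeks. SAP 20.6.1 counts it in 3.2 only if the schedule is q12w and "the duration of interval between injections is above or equal to 12 weeks". SAP 5 says the analysis follows the protocol and lists no change. SAP 12.1 separately tabulates patients dosed under each schedule, without an interval cut-off.

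**The concern.** The 12-week cut sits in the middle of the range the protocol permits for a q12w interval. A q12w injection given one day early within its window makes an 83-day interval, which the protocol wording files in the 8-to-under-12-week band. One such interval is enough to count the eye in 3.1.

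Two things are at stake. First, under the protocol wording 3.1 would take in most on-schedule q12w eyes and could not stand as the q8w share. Second, the protocol wording and the SAP derivation are different quantities under one endpoint label. A programmer could defend either, and the reported 3.1 would differ greatly. The SAP route has a smaller fault of its own: an in-window q12w interval shorter than 12 weeks fails the 3.2 cut and is barred from 3.1 by the schedule condition, so it counts in neither.

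**Working it through.** The documents give no expected percentage for 3.1 or 3.2, so there is no stated figure to reproduce.

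**Inputs.** From Protocol 7.2: q12w injections at Weeks 8, 20, 32 and 44 (three 12-week intervals after loading); q8w injections at Weeks 8, 16, 24, 32, 40 and 48 (five 8-week intervals). From Table 7-1: ±7 days per visit. The distribution of visits inside the window is not given. I assume independent whole-day deviations and vary their shape.

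**Permitted intervals.** Two visits at ±7 days each give nominal ±14 days.
- q12w: 84 ± 14 = 70 to 98 days (10 to 14 weeks).
- q8w: 56 ± 14 = 42 to 70 days (6 to 10 weeks).

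**Protocol wording, q12w eye, uniform over ±7 days.** Four visits with 15 possible days each give 15⁴ = 50,625 combinations.
- 3.1 is not met only if the four deviations never decrease: C(18,4) = 3,060. P(3.1) = 1 − 3,060/50,625 = 94.0%.
- 3.2 is not met only if they strictly decrease: C(15,4) = 1,365. P(3.2) = 1 − 1,365/50,625 = 97.3%.
- Both met: 1 − 0.0604 − 0.0270 = 91.3%.
- One given interval under 84 days: 105/225 = 46.7%.

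**Other timing assumptions, q12w eye.**

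| Visit timing | Meets 3.1 (protocol wording) | Three-interval eye missed by 3.2 | Single-interval eye missed by 3.2 |
|---|---|---|---|
| Uniform ±7 days around the nominal week | 94.0% | 2.7% | 46.7% |
| 50% on the nominal day, rest uniform ±7 | 80.1% | 0.8% | 35.0% |
| 80% on the nominal day, rest uniform ±7 | 44.8% | 0.07% | 16.8% |
| Timed from previous injection, uniform ±7 | 84.8% | 10.2% | 46.7% |
| Timed from previous injection, 80% exact | 25.5% | 0.08% | 9.3% |

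The first three rows are exact enumerations. For the 80% row, the single-interval figure is (1 − P(tie))/2, with P(tie) = 0.8133² + 14 × 0.0133² = 0.664. The last two rows use q = 7/15 = 0.467 and q = 0.2 × 7/15 = 0.093 per interval, giving 1 − (1 − q)³ for 3.1 and q³ for the three-interval miss.

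**q8w eye.** No in-window interval reaches 84 days, so 3.2 is never met. With five intervals, 3.1 is met by more than 99.9% (uniform ±7 days). A single in-window q8w interval falls below 8 weeks with the same 46.7% probability, so the lower cut has the same weakness for an eye with only one q8w interval.

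**Study level, for illustration.** Protocol section 5 quotes 56% and 51% of eyes maintained on q12w in the two pivotal trials. I use these only as plausible q12w shares, with all visits in window and uniform ±7 days.

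| | q12w share 56% (q8w 44%) | q12w share 51% (q8w 49%) |
|---|---|---|
| 3.1, protocol wording | 0.56 × 0.940 + 0.44 × 0.9996 = 96.6% | 96.9% |
| 3.1, SAP derivation | 0.44 × 0.9996 = 44.0% | 49.0% |
| 3.2, either | 0.56 × 0.973 = 54.5% | 49.6% |

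**The 8-to-11-week band.** If this means up to 77 elapsed days, it drops 78 to 83 days, which the endpoint includes. If it means completed weeks, the two agree. The SAP does not say. In-window q8w intervals end at 70 days, so only late q8w injections are affected.

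**The case against.** The strongest defence is that the SAP is the operative analysis, and there a q12w-schedule interval cannot enter 3.1. With visits in window, its 3.1 reproduces the assumed q8w share, and its 3.2 falls about 1.5 points short of the assumed q12w share. SAP 12.1 adds a count of patients by schedule. Overlap is also partly intended: both endpoints ask for at least one interval and reallocation is allowed, so they were never exclusive shares. Every percentage here rests on assumed timing.

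Most of that stands. A reader might infer that objective 3 goes unanswered, or that the reported 3.1 will mainly reflect appointment timing. The documents do not support either: the first overlooks the SAP schedule condition and SAP 12.1, and the second describes only the protocol wording. Nor do the cut-offs explain any mismatch with the pivotal trials, whose quoted figures concern eyes maintained on q12w through Week 48, a different quantity.

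What the defence does not remove is the conflict between derivation and endpoint wording inside the SAP, the undeclared departure from the protocol, and the loss of in-window intervals under 12 weeks. The SAP 12.1 table is an exposure summary and does not settle which definition the endpoint uses.

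**Conclusion.** The point holds in limited form. Under the protocol wording, 3.1 is not a q8w share: between about 25% and 94% of on-schedule q12w eyes would also meet it, depending on visit timing. The SAP derivation cures that overlap, but as an unstated change of definition; in the illustration the two versions of 3.1 are about 97% and 44 to 49%.

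The SAP's remaining error is small for eyes with all three q12w intervals: about 0.1 to 3% missed by 3.2, or 10% if visits are timed from the previous injection and spread evenly over the window. It is larger for eyes with one q12w interval through early exit or reallocation: 17 to 47% with visits timed from the nominal week, and 9% in the most favourable case examined. The number of such eyes is unknown. The permitted ranges and the conflict of definitions follow from the documents alone; the percentages depend on the assumed timing. These are descriptive secondary endpoints with no role in the sample size.

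**What to change.** In SAP 20.5 and 20.6:
- Classify each post-loading interval by the eCRF dosing schedule in force for it. State which eCRF entry governs the interval from Week 8 to the first maintenance injection and an interval that spans a reallocation.
- Give the bands in days to match Table 7-1: q8w 42 to 70, q12w 70 to 98, with the schedule deciding a 70-day tie. Show intervals outside these bands separately. Every in-window interval then counts once, so the misses above fall to zero for in-window eyes.
- Report eyes as q8w only, q12w only, or both.
- Keep the literal version (at least 8 and under 12 weeks; at least 12 weeks), without the schedule condition, as a supportive row, and drop the 8-to-11-week phrase.
- Record the change and its reason in SAP 5.

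A single 10-week cut without the schedule condition is simpler but weaker: a late, out-of-window q8w injection at 10 to under 12 weeks would be counted as q12w.

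The cost is two derivation rules and one note; injection dates and dosing schedule are already collected. The downside is that the main derivation departs from the protocol's literal cut-offs after enrolment is complete (SAP 8.1), so it should be fixed before database lock and shown beside the literal version. It changes how intervals are counted, not how patients are dosed.

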#### 7.7 Quality control

#### 7.7.1 Data quality management

Novartis Data Management or/designated CRO will assure database quality processes are followed including review of the data entered into the eCRFs by investigational site staff for completeness and accuracy, and in accordance with the data validation plan.

#### 7.7.2 Data recording and document retention

In all scenarios, the Investigator must maintain source documents for each patient in the study, consisting of the case and visit notes (hospital or clinic medical records) containing demographic and medical information, and the results of any other tests or assessments. All information entered in the eCRF must be traceable to these source documents in the patient's file.

The Investigator must give Novartis (or designee CRO) access to all relevant source documents to confirm their consistency with the eCRF entries. No information in source documents about the identity of the patients will be disclosed.

The Investigator will retain a copy of all source documents and study records in accordance with the local regulations. The Investigator is recommended to contact Novartis before disposing off any study records.

#### 7.7.3 Site monitoring

The monitors appointed by the CRO/Novartis, or Novartis designee will perform all monitoring functions within this clinical study. Monitors will work in accordance with Standard Operating Procedures (SOPs) of Novartis or the CRO, as designated in the contract. Monitors will be responsible for establishing and maintaining regular contact between the Investigator and Novartis. Monitors will also control adherence to the protocol at the Investigator site.

Monitors will evaluate the competence of each study center. Monitors will inform Novartis regarding problems relating to facilities, technical equipment, or medical staff. Monitors will ensure that written informed consent has been correctly obtained from all patients and during the study will ensure that data are recorded correctly and completely.

Formal site monitoring will be performed as described in the Monitoring Plan for this study.

Novartis Data Management/designated CRO will ensure compliance monitoring.

#### 7.8 Limitations of the research methods

Limitations of Phase IV studies include the potential for observer bias due to lack of blinding and the absence of standardized data collection, and the potential for selection bias due to lack of randomization. However, this is a single-arm, open-label study and the patients would be eligible for this study only after the Investigator makes a decision to prescribe intravitreal brolucizumab.

#### 7.9 Other aspects

Every patient has the right to discontinue study participation at any time, and every patient may be discontinued from the study for any reason beneficial to his/her wellbeing. All data generated up to the time of discontinuation from the study will be analyzed and the reason(s) for discontinuation/withdrawal will be recorded.

Patients must be discontinued from the study in the case of:

- Withdrawal of informed consent to collect or use their data
- Significant safety risk
- The Investigator must record the discontinuation/withdrawal reason in the Case Record Form (CRF). Reasons that a patient discontinues treatment and participation from the study are considered to constitute one of the following:
- Adverse event(s)
- Unsatisfactory therapeutic effect
- Subject's condition no longer requires study treatment
- Subject withdrew consent
- Lost to follow-up
- Administrative problems
- Death

Patients who discontinue brolucizumab treatment should be asked to return for an early discontinuation assessment. For patients who are lost to follow-up (i.e. those patients whose status is unclear because they fail to appear for study visits without stating an intention to withdraw), the Investigator should show "due diligence" by contacting the patients and asking them to return for a final assessment. Every effort should be made to obtain the reason for discontinuation.

The Investigator should document in the source documents steps taken to contact the patient, e.g. dates of telephone calls, registered letters, etc.

For the purpose of this study, the study drug brolucizumab will be provided free of costs for the patients in this study.

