#### 7 **Research methods**

#### 7.1 Study design

This is a prospective, multi-center, open-label, interventional phase IV clinical study. The study treatment i.e. brolucizumab will be prescribed in terms of the marketing authorization; the assignment of the patient to the therapy will be decided within the current practice and the medical indication, and will clearly be separated from the decision to include the patient in the study.

All patients with nAMD who are planned to be treated with brolucizumab and have provided informed consent may be enrolled in this study. The treatment period for each patient will be 56 weeks after the start of brolucizumab treatment. Study visits will be scheduled at week 4, week 8, week 16, and thereafter at intervals of 8 weeks or 12 weeks after disease activity assessment at week 16. If the investigators require more frequent follow-up visits, it can be done according to their discretion and clinical judgment. The study drug will be provided free of cost to the patients in the study. Any patient who suffers from intra-ocular inflammation (IOI) during the study period would not be re-challenged with brolucizumab.

Data originating from assessments and evaluations performed will be collected from the patient's medical records at Baseline (BL), i.e. start of brolucizumab treatment, week 4, week 8, week 16, week 20, week 24, week 32, week 40, week 44, week 48 and at week 56.

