#### 10. Participant disposition and withdrawal

#### 10.1 Variables and derivations

End of trial classifications are defined as follows:

- Screening failure: Patient signed an informed consent form but has not satisfied inclusion and exclusion criteria.
- Enrolled Patients: Patient signed an informed consent form and has satisfied inclusion and exclusion criteria.
- Discontinued patients: patients who discontinued the trial, as indicated in the "Study Completion" eCRF form, will be assumed to be discontinued patients
- Completed trial: Patients who completed the trial, as indicated in the "Study Completion" eCRF form, will be assumed to have completed the trial.

The following parameters will be summarised for the patient's disposition table as per eCRF

- Number of screened patients
- Number of screening failure patients
- Number of enrolled patients
- Number of patients enrolled but not received the first dose of Brolucizumab
- Number of patients received all dose of Brolucizumab
- Full analysis Set (FAS)
- Number of completed patients
- Number of discontinued patients

Patient's primary reason for discontinuation (reasons mentioned in eCRF study completion form) which is as follows:

- Adverse event
- Unsatisfactory therapeutic effect
- o Subject's condition no longer requires study treatment
- Subject withdrew consent
- Lost to follow-up
- Administrative Problems
- Switch Agent
- o Death
- o Other

Derivation:

- If patient status is indicated as "screen failure" in the eCRF screen failure form, then respective patients will be counted as screen failure.
- If the question "Was written informed consent obtained" = "Yes" from the informed consent eCRF form and the question "Did the subject meet all eligibility criteria" = "Yes" then respective patients will be counted as enrolled patients.
- If the question "Did the patient complete the study" = "No" from the Study Completion eCRF form, then respective patients will be counted as discontinued patients.
- If the question "Did the patient complete the study" = "Yes" from the Study Completion eCRF form, then respective patients will be counted as completed patients.

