#### Derivations:

- The question "Relationship to study drug" is answered as "Yes" then respective AEs will be considered as Related AE.
- The question "Was the adverse event serious" is answered as "YES" then respective AE will be considered as serious AEs.
- Subject's primary reason for discontinuation is "Adverse Event" then we will consider it as AEs leading to Discontinuation from the study.
- Subject's primary reason for discontinuation is "Death" or AE Outcome is "FATAL" then we will consider it as AEs leading to death.
- Subject's primary reason for discontinuation is "Death" or AE Outcome is "FATAL" and "Relationship to study drug" is answered as "Yes" then we will consider it as Related AEs leading to death.

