#### Derivation:

- Timeframe: The first brolucizumab administration date to Visit 11 (week 56)
- If the question from eCRF, "Treatment Emergent AE" = "Yes", then corresponding events will be considered as TEAEs.
- Ocular and systemic AEs.
- If the question from eCRF, "Relationship with study drug" = "Yes", then corresponding events will be considered as suspected AEs related to the study medication.
- If the question from eCRF, "Was the adverse event serious" = "Yes", then corresponding events will be considered as serious AEs.
- If the question from eCRF, "What is the outcome of this adverse event" = "Fatal", then corresponding events will be considered as AEs leading to death.
- If the question, "Primary Reasons for Discontinuation" = "Adverse event", then corresponding events will be considered as AEs leading to discontinuation from the study.

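### The SAP adds undefined Switch Agent and Other categories to the protocol's closed list of discontinuation reasons, so some exits may be missed under their cause

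*Protocol*

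**What the plan says.** Protocol 7.9 states: "Reasons that a patient discontinues treatment and participation from the study are considered to constitute one of the following". Seven reasons follow: adverse event, unsatisfactory effect, treatment no longer needed, withdrawn consent, loss to follow-up, administrative problems and death. The same section says that "the reason(s) for discontinuation/withdrawal will be recorded", so more than one may be noted. Protocol 7.6.4 plans the table: "The number (%) of patients who discontinue prematurely prior to 56 weeks will be tabulated including the reasons for discontinuation".

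SAP 10.1 introduces its list with "Patient's primary reason for discontinuation (reasons mentioned in eCRF study completion form) which is as follows". It keeps all seven protocol reasons, including "Unsatisfactory therapeutic effect", and adds *Switch Agent* and *Other*. Neither is defined. SAP 5 says that the analysis follows the protocol and leaves any deviation to the study report; it does not mention the longer list.

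The primary reason also feeds a safety summary. In SAP 15.1, if it is *Adverse Event*, "then we will consider it as AEs leading to Discontinuation from the study". SAP 19.1.1 repeats the rule for the primary endpoint: when the reason is *Adverse event*, "then corresponding events will be considered as AEs leading to discontinuation from the study". Neither section gives another route into that row.

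**The concern.** The protocol's reasons for leaving are causes or events. *Switch Agent* is an action taken afterwards. It can be true at the same time as *Adverse event* or *Unsatisfactory therapeutic effect*, yet only one primary reason is tabulated and no rule says which takes precedence. *Other* can hide a cause in the same way unless the cause is specified.

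In a single-arm study, the reasons for stopping are one of the main ways a reader sees intolerance and lack of effect. They also show why values are missing at week 56, since Protocol 7.6.1 and SAP 8.2 carry the last observation forward whatever the reason. Two outputs are at stake: the disposition table, and the row for adverse events leading to discontinuation, which SAP 19.1.1 lists as a characteristic of the primary endpoint.

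**Working it through.** The documents state no figure to reproduce on this point. The check compares the two lists and traces where the primary reason is used.

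**1. The lists side by side**

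| Reason | Protocol 7.9 | SAP 10.1 |
|---|---|---|
| Adverse event | yes | yes |
| Unsatisfactory effect | yes | yes |
| Treatment no longer needed | yes | yes |
| Consent withdrawn | yes | yes |
| Lost to follow-up | yes | yes |
| Administrative | yes | yes |
| Death | yes | yes |
| Switch Agent | no | yes |
| Other | no | yes |
| Total | 7 | 9 |

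9 − 7 = 2 added categories. Neither document defines them or ranks them against the other seven.

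**2. Where the primary reason is used**

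- Disposition table (SAP 10.1 and 10.2): one primary reason per discontinued patient.
- Events leading to discontinuation from the study (SAP 15.1 and 19.1.1): primary reason only.
- Events leading to death (SAP 15.1): primary reason or a fatal outcome. This rule has a second source; the discontinuation rule has none.
- Treatment-emergent, serious and related events (SAP 19.1.1): taken from their own eCRF questions and independent of the primary reason.
- Action taken (SAP 15.1): recorded per event, with a category for permanent discontinuation of study treatment because of that event. It is also independent of the primary reason.

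**3. Two cases**

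- *A patient stops after an adverse event, moves to another drug and leaves the study.* Coded *Adverse event*, the patient appears under that cause and in the discontinuation row. Coded *Switch Agent*, the patient appears in neither. The event still counts as treatment-emergent and, if the action was recorded, appears under action taken.
- *A patient leaves for another drug because of lack of effect.* Coded *Unsatisfactory therapeutic effect*, the cause is visible. Coded *Switch Agent*, it is tabulated nowhere, because no other summary gives lack of effect as a reason for leaving.

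**4. Scale**

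SAP 8.1 reports 105 patients enrolled. SAP 10.2 bases the disposition percentages on patients who received a first dose. Assume that all 105 were dosed. For k patients coded *Switch Agent* or *Other* instead of the cause, the shift in that cause is 100 × k / 105:

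- k = 1: 100 / 105 = 0.95 points
- k = 3: 300 / 105 = 2.86 points
- k = 5: 500 / 105 = 4.76 points

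The values of k are illustrative. For comparison, Protocol 7.4 allows 105 − 95 = 10 patients for attrition, so one misrouted patient would be a tenth of the planned exits. That allowance covers dropout and loss to follow-up of any kind and does not estimate the number of switches.

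**The case against.** The strongest reply is that nothing need be lost. SAP 10.1 keeps both causes on the list and asks for the primary reason, so a site that records the cause will be counted correctly. The Study Completion form is not among the documents; it may carry instructions or a free-text field. SAP 10.2 lists early withdrawals and SAP 23.4.1 lists all eCRF data, so a reader could match exits to events patient by patient. Protocol 7.6.5 promised a summary of events causing discontinuation of study *drug*, and the action-taken item in SAP 15.1 comes close to that. SAP 5 leaves room to describe deviations in the study report. No estimand, test or sample size is touched.

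Much of this stands. A reader might infer that switched patients are counted under neither cause. The documents do not support that: the loss arises only if the site chooses one of the added categories.

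A reader might also infer that the loss is systematic for intraocular inflammation, because Protocol 7.1 says: "Any patient who suffers from intra-ocular inflammation (IOI) during the study period would not be re-challenged with brolucizumab". That sentence bars further brolucizumab. It does not say that the patient leaves the study, receives another agent, or is coded in any particular way.

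The objection does not remove the gap in the rule. Listings are not a tabulation. Action taken appears in an overview, while SAP 15.2 sends the discontinuation summary by system organ class and preferred term to section 19, which uses the primary reason alone. Lack of effect has no second tabulated source.

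**Conclusion.** The point holds as a possible misclassification. The SAP departs from the protocol's closed list without declaring it, and two undefined categories compete with real causes in a field where one answer is tabulated. The disposition table can therefore understate exits for adverse events or lack of effect, and the discontinuation row of the primary endpoint can understate the former.

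It should not be read as an undercount of treatment-emergent adverse events: their incidence, severity, seriousness and relatedness do not depend on this field.

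The number of patients affected cannot be computed, because the documents give no count of switches. The only size available is about 0.95 percentage points per misrouted patient, assuming 105 dosed patients. This is an inexpensive improvement to reporting and does not threaten the study's conclusions.

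**What to change.** - Before database lock, query the underlying protocol cause for every patient coded *Switch Agent* or *Other*, and tabulate the patient under that cause. If a reply fits none of the seven, report the stated cause and declare the extra row as an addition to the protocol.
- Show whether the patient moved to another agent (yes/no) as a separate row in the disposition table.
- In SAP 15.1 and 19.1.1, derive adverse events leading to discontinuation from the event-level action taken (study treatment permanently stopped because of the event) as well as from the primary reason. Label the row as covering drug or study, since the two sources differ on this.
- Declare the longer list and its handling in SAP 5.

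The cost is a few site queries, one extra table row and some SAP wording. No visits, patients or treatment decisions change. The SAP is dated 10 May 2023 and Protocol 4 plans the end of data collection for 1 December 2023, so the queries fit the planned timeline.
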